## PROTOCOL SYNOPSIS

|   |   |
|---|---|
| TITLE                                | Prospective Randomised Open-label Trial to Evaluate risk faCTOR management in patients with Unruptured intracranial aneurysms.  |
| SHORT TITLE                          | PROTECT-U   |
| CLINICAL TRIAL CODE                  | PROTECT-U   |
| EUDRACT NO.                          | 2017-000514-35  |
| INDICATION                           | Intradural saccular unruptured aneurysm   |
| OBJECTIVES                           | The primary aim of this study is to assess the hypothesis that a strategy with low-dose ASA (81-100mg/day) and intensive blood pressure treatment (targeted systolic blood pressure below 120mmHg) with weekly measurements using a home blood pressure measuring device reduces the risk of aneurysm rupture or growth compared with standard care (i.e. no ASA, blood pressure management according to guidelines which usually advise treatment if systolic blood pressure exceeds 140mmHg, and no home device for weekly blood pressure measurements).  |
| PHASE                                | III   |
| INVESTIGATIONAL MEDICINAL PRODUCT(S) | Acetylsalicylic acid (ASA), 81-100mg once per day   |
| STUDY DESIGN                         | Multinational, phase III multicenter, randomised, controlled trial with a PROBE design (prospective, randomised, open-label trial with blinded outcome assessment)  |
| STUDY POPULATION                     | 
Inclusion Criteria
 
 
• Patient with at least one intradural, saccular unruptured aneurysm in whom it is decided not to intervene with preventive neurosurgical or endovascular aneurysm repair and who are monitored on a regular basis for aneurysm growth
 
• 18 years or older
 
• Last aneurysm imaging with either CTA/MRA within the last 3 months
 
• Ability of subject to understand character and individual consequences of clinical trial
 
• Not legally incapacitated
 
• Written informed consent (must be available before enrolment in the trial)
 
 |

|                       |   |
|-----------------------|---|
|                       | 
 
For women with childbearing potential adequate contraception
 
  |
|                       | 
Exclusion Criteria
 
 
All non-saccular UIAs or aneurysms related to arteriovenous malformations
 
Daily ASA already prescribed for another indication
 
Use of a vitamin K antagonist or direct oral anticoagulant (DOAC) at baseline
 
History of hypersensitivity/allergy to ASA or to any other drug with similar chemical structure or to any excipient present in the pharmaceutical form of ASA
 
History of asthma induced by ASA or other anti-inflammatory drugs
 
Other contra-indications for low-dose ASA (81 mg - 100 mg per day) not yet mentioned, (e.g. bleeding disorders, , gastric ulcers and/or intestinal ulcers, acute liver failure of kidney failure, severe heart failure, treatment with methotrexate in a dosage 15 mg/week or above)
 
Use of another platelet aggregation inhibitor, which in combination with ASA would give an unacceptable risk of side effects/complications
 
Chronic kidney disease stage IV and V (GFR < 30 mL/min/1.73 m^2)
 
Pregnancy and lactation
 
Participation in any other interventional clinical trial
 
Life-expectancy <3 years
 
 |
| SAMPLE SIZE    | 
To be assessed for eligibility: (n = 2500)
 
To undergo screening examination: (n=970)
 
To be assigned to the trial: (n = 776)
 
To be analysed: (n = 705)
 
Assuming a risk reduction of 45% for the primary outcome measure and the risk to have a primary outcome event at three years of 15% in the standard treatment group and 8.25% in the intensive treatment + ASA group, <math>\alpha=0.05</math> and <math>\beta=0.20</math>, 353 patients are needed in each group. Assuming a dropout rate of 10%, we will need to assign 776 patients to the trial so that 705 patients can be analysed.
  |
| TRIAL DURATION | 
Total trial duration: [162 months]
 
Duration of clinical phase: [144 months]
 
Beginning of the preparation phase: [Q2 2017]
 
FSI (first subject in): [Q3 2017]
 
LSI (last subject in): [Q2 2026]
   |

|                             |  |
|-----------------------------|--|
|                             | LSO (last subject out): [Q2 2029]
DBL (database lock): [Q3 2029]
Statistical analyses completed: [Q4 2029]
Trial report completed: [Q2 2030]  |
| STATISTICAL ANALYSIS | 
Primary endpoints:
 
Aneurysm rupture (i.e. aneurysmal subarachnoid hemorrhage, SAH) or growth (increase in any aneurysm diameter by <math>\geq 1\text{mm}</math>) on serial imaging (either two MR or CT angiographies) within <math>36\pm 6</math> months from randomization
 
Secondary endpoints:
 
 
• Any growth or rupture of aneurysm during follow-up irrespective of the duration of trial participation
 
• Difference of aneurysm volume (defined as increase of aneurysm volume in computerized measurements from source images by <math>>10\%</math> and <math>>3\text{mm}^3</math> or aneurysm shape (e.g. development of daughter sac)
 
• Development of de novo aneurysm on serial imaging
 
• Clipping/coiling during the study period
 
• Any ischemic or haemorrhagic stroke, defined as clinical symptoms of stroke AND a compatible lesion on imaging (either plain head CT / CT perfusion / MRI)
 
• Myocardial infarction defined as increase of Troponin, CKMB and/or presence of new significant Q waves obtained in ECG
 
• Vascular death (including fatal stroke, fatal myocardial infarction, sudden death)
 
• Death from all other causes
 
• Major spontaneous bleeding requiring hospitalisation defined as substantially disabling bleeding, intraocular bleeding leading to the loss of vision, or bleeding necessitating the transfusion of at least 2 units of erythrocyte concentrates achieved
 
• Blood pressure; any data on blood pressure management used
 
• Safety aspects (adverse and serious adverse events, including those mentioned above)
 
• Quality of life
 
 
We will compare the occurrence of outcome events in the two groups in terms of the risk ratio (RR), which will be obtained by means of a Poisson model. The precision of the RR estimates will be described with 95% confidence intervals obtained from the Poisson model. Our primary analyses will be based on the intention-to-treat principle. We plan subgroup analyses according to
 |

|   |   |                               |
|---|---|-------------------------------|
| Clinical Trial Code: Protect-U
EudraCT: 2017-000514-35 | Trial Protocol
Version 07 - August 23 - 2022 | Page 13 of 62
CONFIDENTIAL |
|---|---|-------------------------------|

|                          |  |
|--------------------------|--|
|                          | age, sex, history of previous rupture of another aneurysm, aneurysm size, location and morphology.   |
| NUMBER OF CENTRES | up to 30 (Germany, the Netherlands, Canada, Finland, other countries)  |
| FINANCING         | Non-commercial: [name] Foundation (Mannheim, Germany), Dutch Heart Foundation (Netherlands), Phoenix foundation                            |
| Other support     | Blood pressure measurement devices made available for the time of the trial by Omron Healthcare Europe B.V., [name], Netherlands |

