## 6.2 Baseline Visit

The following are key elements of the baseline visit:

- Confirmation that all inclusion- / exclusion criteria are satisfied
- If a recent (<6 months) GFR (determined at the lab of the trial center or at another lab that provides a copy of the appropriate lab certificate) is not available, a blood test will be done to measure GFR after informed consent has been obtained.
- Verification of participant contact information
- Completion of the study randomization procedure using an online randomization tool, as soon as lab values needed for inclusion (e.g. negative pregnancy testing) are available.
- Collection of the following baseline characteristics by history taking: history of hypertension / ischemic stroke / intracerebral hemorrhage / subarachnoid hemorrhage / myocardial infarction / peripheral vascular disease / polycystic kidney disease, tobacco smoking history including number of packyears of smoking and current number of cigarettes per day, medication use, alcohol consumption, number of first degree and second degree relatives with an intracranial aneurysm (either unruptured or ruptured), and an EQ-5D-5L questionnaire is completed by the patient.
- Collection of aneurysm characteristics based on reviewing medical data: 1) number of intracranial aneurysms; 2) anatomical site(s) of the UIA; 3) maximum UIA diameter; and 4) aneurysm shape.
- A blood pressure will be measured in sitting position.
- If the time between screening visit and baseline visit exceeds so much time (depending on the cycle of the patient) that another pregnancy test is necessary, an additional rapid test will be performed.
- Clinical chemical parameter may be controlled, if the investigator decides they are necessary.
- A baseline assessment for symptoms of potential adverse effects of ASA is performed prior to beginning the therapy.
- Trial medication is provided to patients randomized to the intervention group.

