### 9.3 Statistical Methods

Baseline characteristics will be summarized as means with standard deviations or proportions, as appropriate. In the primary analysis we will quantify the treatment effect of a strategy aimed at risk factor modification by intensive blood pressure treatment, monitoring with a blood pressure measuring device, and acetylsalicylic acid (ASA) on the risk of aneurysm rupture or growth, which is an established surrogate for the risk of rupture, compared with standard blood pressure treatment and no ASA.

We will compare the occurrence of outcome events in the two groups in terms of the risk ratio (RR), which will be obtained by means of a Poisson model. The precision of the RR estimates will be described with 95% confidence intervals obtained from the Poisson model. Our primary analyses will be based on the intention-to-treat principle. Patients will be censored in case of death from causes other than aneurysm rupture. In addition to crude analyses, we will do an analysis adjusted for the main risk factors of the primary outcome: aneurysm size, shape, location, age and smoking status. For our secondary analyses in which the timing of the outcome event is not prespecified but all follow-up data are taken into account, we will calculate hazard ratios using Cox regression analyses. Final details will be specified in the Statistical Analysis Plan.

We plan the following subgroup analyses: age ( $\leq 55$  versus  $> 55$  years), sex, and type (with or without previous rupture of another aneurysm), size (1.0-4.0 mm versus  $\geq 4.1$  mm), aneurysm location (posterior communicating artery / anterior communicating artery / posterior circulation versus all other aneurysms) and morphology of aneurysm (regular versus irregular shape).

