#### 9.4 Interim Analyses

The DSMB will review data of two interim analyses on the primary outcome to assess the strength of the efficacy data. The first interim analysis will be carried out after 235 patients have had their 3-year outcome assessment; the second one after 470 patients have these outcome data. The DSMB will also check the assumptions for sample size calculations. The DSMB can recommend the Steering Committee of the PROTECT-U trial to:

- Adjust the sample size
- Early terminate the study when there is clear and substantial evidence of benefit, based on a significant (with alpha 0.1%) reduction in aneurysm growth and rupture (according to the Peto approach of interim analysis with alpha 5% at final analysis); a different stopping rule may be suggested by the DSMB.
- Early terminate the study when there is evidence of severe harm based on SAE reporting, outcome, and case fatality
- Early terminate the study in case accrual rates are too low to provide adequate statistical power for identifying the primary endpoint
- The Steering Committee and the DSMB will agree on the approach to early termination (stopping rules) and the statistical methods used for efficacy evaluation beforehand. This approach will be described in a separate DSMB charter.

After the inclusion of 100, 300 and 600 patients, and if needed after later time points, the proportion of patients with aneurysms <3 mm will be analysed. Patients in this subgroup have the lowest risk of aneurysm growth and rupture. Care should be taken that the proportion of patients with aneurysms <3 mm does not exceed 30% of the total study cohort, so that the power calculation is not jeopardized. With 776 patients to be included, no more than 230 patients with aneurysms <3 mm should be included.

Because the first formal interim analysis will take place after 235 patients reached the 36 months visit, an additional two preliminary interim analyses will be done based on the first 235 and 470 patients, at the timepoint 12 months after randomization of subject 235 and 470 respectively, with all routinely obtained follow-up data available. To this end local reports on aneurysm growth will be used.

Interim analysis reports will be prepared and supported by a member of the data management team of the KKS and then forwarded to the DSMB. The results will not be disseminated inside or outside the study team.

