## 10 DATA MANAGEMENT

### 10.1 Data Collection

A study specific database will be set up using ClinCase™ and validated for this project with coded information of the participants who are included in the study. After informed consent, subjects will be registered in a secured database managed by the KKS using unique participant identification numbers. The patient ID is composed of a site number and the randomization number generated by the online randomizing tool. Only authorized study personnel will have access. Hence, the names and patient numbers of participants will be replaced by a study code for all study related procedures and will not be directly convertible to the participant. This code list is exclusively possessed by PI and investigators at each trial centre, and saved in a separate, secured database. All data will be collected according to the applicable national data protection, privacy and secrecy laws.

Study data collected in the e-CRF will consist of:

- Study characteristics: study number, date of randomization, treatment allocation.
- Data collected at baseline: date of birth, sex, history of hypertension / ischemic stroke / intracerebral hemorrhage / subarachnoid hemorrhage / myocardial infarction / peripheral vascular disease / polycystic kidney disease, medication use, tobacco smoking history including number of packyears of smoking and current number of cigarettes per day, alcohol use, recent (<6 months) GFR, number of first degree and second degree relatives with an intracranial aneurysm (either unruptured or ruptured), date and type of last aneurysm imaging before randomization, seated blood pressure, number of aneurysms, aneurysm size, aneurysm location, aneurysm shape, EQ-5D-5L.
- Data collected during the trial: smoking status, seated blood pressure, drug adherence (by counting unused tablets), occurrence of adverse events, concurrent medication, date(s) and type(s) of subsequent imaging, occurrence of aneurysm growth or rupture during trial according to local investigator, occurrence of cardio-/cerebrovascular outcomes during the trial, EQ-5D-5L.

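### Section 9.3 examines effect modification by age and aneurysm size through one cut each, which loses information if the effect changes steadily with size; exploratory continuous interactions should be added beside the cuts

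*Protocol*

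**What the plan says.** The synopsis names the subgroup factors without cut-points: "age, sex, history of previous rupture of another aneurysm, aneurysm size, location and morphology". The cuts are in section 9.3. Age and sex come first: "We plan the following subgroup analyses: age ( $\leq 55$ versus $> 55$ years), sex". Diameter follows: "size (1.0-4.0 mm versus $\geq 4.1$ mm".

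Both variables are available as numbers. Section 6.2 collects "3) maximum UIA diameter; and 4) aneurysm shape", and section 10.1 lists "Data collected at baseline: date of birth, sex, history of hypertension" among the baseline items. Age and size also enter the adjusted analysis in section 9.3, but as risk factors for the outcome and not as modifiers of the treatment effect. The section leaves final details to the SAP.

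Section 9.4 uses a different size boundary. It monitors the share of aneurysms under 3 mm and says of them: "Patients in this subgroup have the lowest risk of aneurysm growth and rupture". It limits this class to 30% of the cohort: "no more than 230 patients with aneurysms <3 mm should be included".

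**The concern.** A single cut treats all patients on one side as alike. A patient with a 1.5 mm aneurysm is pooled with one at 3.9 mm, and 4.2 mm with 9 mm. Any change of effect within a half is averaged away, although the measurements that could show it are in the database.

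Size matters in this trial. Sections 1.1 and 1.3 present it as a search for low-risk treatment for small aneurysms. The budget impact scenarios in section 9.3 run from all patients with a known aneurysm to those with larger aneurysms only. Readers will ask whether the benefit depends on diameter. The planned split is a blunt way to answer, and it does not separate out the class under 3 mm that section 9.4 follows during recruitment.

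**Working it through.** **Inputs from the protocol.** Section 9.1: 15% versus 8.25% at three years (risk ratio 0.55), alpha 0.05, power 80%, 353 per group, 776 assigned with 10% dropout. Section 9.3: risk ratio from a Poisson model, and the two cuts. Section 9.4: at most 230 of 776 patients under 3 mm.

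**Assumed, because the protocol gives no figures.** The distribution of aneurysm size and the shape of any interaction.

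**1. The protocol's own sample size.** Two proportions, two-sided 5%, pooled variance under the null, mean risk 0.11625:

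n = [1.960 × √(2 × 0.11625 × 0.88375) + 0.8416 × √(0.15 × 0.85 + 0.0825 × 0.9175)]² / 0.0675² = (0.8884 + 0.3794)² / 0.004556 = 352.8, so 353. This matches.

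**2. Expected events.** 353 × 0.15 + 353 × 0.0825 = 52.9 + 29.1 = about 82.

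**3. Information kept by one cut.** For a normal covariate and a linear interaction, the fraction kept is φ(c)² / [p(1 − p)], where p is the share below the cut and c the matching normal quantile.

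- p = 0.5: 0.3989² / 0.25 = 0.64 (36% lost)
- p = 0.3: 0.3477² / 0.21 = 0.58 (42% lost)
- p = 0.2: 0.2800² / 0.16 = 0.49 (51% lost)

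The calculation applies to age as well as to log size. It is the only support available for age, since the protocol gives no age distribution.

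**4. Power for a size interaction, monotone gradient.** Simulated trials, Poisson model with robust variance, two-sided 5%, log risk ratio linear in log diameter. Two settings:

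- A: 698 analysed (776 × 0.9), log-normal size with median 4 mm and 30% under 3 mm, so the SD of log size is (ln 4 − ln 3) / 0.524 = 0.549; risk ratio 0.55 at 4 mm; 1,500 runs.
- B: 706 analysed, medians 3.7 to 4.8 mm, log-SD 0.42 to 0.50 (17–31% under 3 mm), average risk ratio 0.55; 2,000 runs.

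A slope per SD converts to a fold change between the 10th and 90th size percentiles as exp(2.563 × slope).

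| Fold change in risk ratio | Slope per SD | Setting | Cut at 4 mm | Continuous |
|---|---|---|---|---|
| 2.0 | 0.27 | B | 15–18% | 24–27% |
| 2.8 | 0.4 | A | 27% | 53% |
| 3.6 | 0.5 | A | 44% | 73% |
| 4.0 | 0.54 | B | 46–54% | 67–75% |
| 4.7 | 0.6 | A | 61% | 89% |
| 6.0 | 0.70 | B | 67–80% | 89–95% |

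A repeat at the three setting-A slopes gave 28%, 41% and 59% with the cut and 52%, 74% and 89% with the continuous term. These slopes are not small: at 0.5 per SD the risk ratio is 0.33 at 2.3 mm and 0.91 at 6.9 mm. With no interaction, rejection was 5.7% (continuous) and 5.3% (cut) in A, and 5.3–6.8% and 4.2–5.6% in B. A small part of the advantage in B is therefore a slightly liberal test.

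**5. Power when the effect is a step.** 706 analysed, median 3.8 or 4.0 mm, 1,500 runs.

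| True pattern | Cut at 4 mm | Continuous | Cut at 3 mm |
|---|---|---|---|
| Risk ratio 1.0 under 3 mm, 0.45 above | 13% | 22% | 34–35% |
| Risk ratio 0.9 up to 4 mm, 0.35 above | 57–59% | 43% | 24–26% |

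**6. What a row under 3 mm could show.** At the cap, 115 per arm, with full design rates: 17.25 and 9.49 events. SE of the log risk ratio = √(1/9.49 − 1/115 + 1/17.25 − 1/115) = 0.382. The 95% CI is 0.55 × exp(±1.96 × 0.382) = 0.26 to 1.16. Because section 9.4 says this class has the lowest risk, the actual interval would be wider.

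**The case against.** Four arguments stand against this point.

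- **The SAP may supply the remedy.** Section 9.3 names subgroups but fixes no interaction test and no rule for drawing conclusions from them, so a continuous term or an extra row would contradict nothing. That stands. A reader might infer that the effect under 3 mm will never be shown; the protocol does not support that. What remains is that the cuts are written into the protocol, and they are the only treatment-effect analyses by age and size that it describes.
- **The simulation in step 4 favours the continuous term.** The data were generated in the form that this term fits. That is fair, and step 5 shows the reverse case: the cut wins if the true step is at 4 mm. It is why the cuts should stay and non-linearity should be checked.
- **The different boundary in section 9.4 is not a contradiction.** A reader might take it as one. Section 9.4 follows the class under 3 mm to protect the event rate, which concerns absolute risk. Nowhere does the protocol say that the relative effect differs there, and a recruitment cap and a subgroup cut need not share a threshold.
- **The cut is not the main reason an interaction would be missed.** With about 82 events, a twofold gradient goes undetected about three times in four even with the continuous term. For age there is only the general argument in step 3, and nothing in the protocol suggests that the effect depends on age. A claim that the cut would hide an age effect therefore goes too far.

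The budget impact text, finally, does not say that its scenarios will use size-specific efficacy. It makes the question relevant and no more.

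**Conclusion.** The point holds as a modest improvement to a stated method. The primary analysis and the sample size are untouched. If the effect changes monotonically with diameter, the single cut keeps between about half and two thirds of the information. Power for moderate-to-steep gradients then falls from about 52–89% to about 27–61%. This rests on an assumed log-normal size distribution and a log-linear interaction. For a modest gradient both approaches are weak, and for a step at 4 mm the planned cut is the better test. The mismatch with the class under 3 mm is a gap in presentation. For age, the loss of information is general and has not been quantified for this trial. The defect sits in section 9.3; the synopsis line lists factors only and is not wrong.

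**What to change.** In section 9.3, or in the SAP before outcome data by arm are seen:

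- Add exploratory interactions of treatment with log diameter and with age to the Poisson model, both on the continuous scale, with a check for non-linearity.
- Report estimated risk ratios with confidence intervals at values chosen in advance, for example 2, 3, 5 and 7 mm.
- Keep the two-level subgroups as specified, shown alongside.
- Add a descriptive row for aneurysms under 3 mm, with a note that it will be imprecise (step 6).

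The cost is a few sentences and a little more analysis; no new data, visits or patients. The continuous term has lower power than the cut if the effect really steps at 4 mm, which is a reason to report both. Section 9.3 requires the SAP to be authorised before the database is opened, and lock is planned for Q3 2029, so there is time.
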